Scheduled Gradual Reduction (SGR) helps users to self-regulate and practice restraint in response to tobacco use cues and has great potential to improve cessation rates. Scheduled Gradual Reduction (SGR) may be especially efficacious in helping smokeless tobacco users to quit as it addresses self-regulation of situational cues to chew. SGR is a reduction-based cessation method that first assesses smokeless tobacco user patterns, then gradually reduces the number of chews/dips used per day by lengthening the time interval between use ending with a definitive quit date at the end of the reduction period. SGR has been minimally studied in smokeless tobacco users.⁹ However, the few studies available demonstrate that SGR promotes cessation among smokeless tobacco users.^{9,25} Our SGR intervention is unique compared to other smokeless tobacco cessation interventions in that it provides chewers with a specific schedule for chewing, encouraging use of chewing restraint techniques during intervals between alerts to chew. Chewing on a schedule has two important functions: (1) nicotine use is evenly spaced to manage withdrawal symptoms; and (2) it provides multiple opportunities to employ restraint, defined as conscious, chronic restriction of chewing based on set limits.²³ Evidence from studies with cigarette smokers have shown that successful use of restraint during reduction is predictive of quitting.⁵ Very few interventions for smokeless tobacco users have addressed self-regulation and restraint through scheduled chewing. Our intervention provides a schedule for chewing and chewers are asked to chew only when alerted. As a result, chewing becomes unlinked from the cues (i.e., psychological, behavioral, and environmental) and smokeless users can learn how to manage cravings using restraint during the reduction period prior to quitting.

[figure not shown]
Our SGR intervention also helps participants manage withdrawal symptoms, an important determinant of cessation success through scheduled chewing that gradually reduces their tobacco use down to zero. The gradual reduction of the SGR intervention provides even spacing between nicotine self-administration leading to the down regulation of nicotine receptors over time.²⁶ Given nicotine dependence is a predictor of smokeless tobacco cessation and smokeless tobacco users report a similar severity of withdrawal symptoms compared to cigarette smokers,²⁷ addressing withdrawal symptoms during a quit attempt is critical

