Mediator: Self-regulation. We will assess self-regulation using the Short-form Self-Regulation Questionnaire, which is a 31 item self-report survey measuring the ability to regulate behavior and achieve goals.⁴⁸ Participants indicate the extent to which they agree with each item using a 5-point Likert scale: 1 (Strongly Disagree), 2 (Somewhat Disagree), 3 (Neutral), 4 (Somewhat Agree), and 5 (Strongly Agree). The measure has a total scale computed by summing the items, with higher total scores indicating increased self-regulation. Internal consistency of the scale is reported to be $\alpha=0.92$.

Mediator: Restraint. We will measure restraint using a modified version of the Smoking Restraint Questionnaire⁴⁹ for smokeless tobacco by replacing all smoking references with smokeless tobacco. The Smoking Restraint Questionnaire is a four-item survey. The two binary questions of the questionnaire are scored 1 (No) and 5 (Yes). The two multiple-choice items are scored from 1 to 5. Total smokeless tobacco restraint is calculated as the sum of the four items. The minimum possible score is 4 and the maximum possible score is 20, with higher total scores indicating higher levels of restraint. Internal consistency of the scale is reported to be $\alpha=0.74$.

Sample Characteristics : Baseline sociodemographic and clinical measures will be collected to describe the characteristics of the total sample and intervention arms. Many of these measures are potential important moderators or mediators of intervention effects that will be explored after the specific aims are fully examined.

- **Demographics and Relevant Biological Variables.** We will assess age, sex, race, education, marital status, and socio-economic status (SES) at baseline using measures adapted from our prior research.
- **Smokeless and other Tobacco Use History.** At baseline, participants will be asked about their tobacco use habit including: number of chews/dips per day, number of quit attempts in the past year, age of chewing/dipping initiation and past use of other tobacco products including electronic cigarettes.
- **Nicotine Replacement Therapy (NRT) Use:** We will ask participants at all follow-up time points if they have used any NRT including the patch, gum or lozenge.

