A text-based reduction intervention for smokeless
tobacco cessation

NCT04315506

01/28/2022

Data Analysis Plan

We will use descriptive statistics to summarize the sample characteristics and study measures collected at baseline and longitudinally. We will perform non-directional statistical tests with the significance level set at 0.05 for all analyses. The primary outcome is self-report smokeless tobacco cessation at month 6 (Aims 1 & 3). Due to the exploratory nature of the mediator analyses, the significance level of 0.05 will not be adjusted for the multiple tests associated with steps for determining mediation (Aims 2 & 3). For the efficacy and mediator analyses we will perform, both intention-to-treat (ITT) and completers analyses. ITT analyses will be the primary analyses and will include all participants randomized to an intervention regardless of treatment or study completion. Completers analyses will include only those participants who complete the month 6 assessment, regardless of level of adherence to the SGR or control intervention. Effect sizes and 95% confidence intervals (CIs) will be reported to address clinical significance for the efficacy and mediator analyses. Analyses will be conducted by our faculty biostatistician [name] (Co-I) to ensure application of rigorous methods and implementation of quality assurance procedures. All data will be stored in REDCap at Duke University and downloaded to SAS Version 9.4 for the statistical analysis.

Handling of Missing Data. Missing smokeless tobacco cessation outcome data will be imputed as “did not quit” for the Aim 1 and 3 primary outcome analyses applying the ITT principle. Aim 2 will apply hierarchical mixed-effects trajectory models to assess change in withdrawal symptoms, craving, self-regulation and restraint. Trajectory methods will allow missing outcome data when estimating participant trajectories. To test the data missing at random (MAR) assumption of trajectory methods, intervention group differences in missing rate at each time point and number of missing values across time will be compared using tests for difference in proportion or cumulative counts. For missing covariate data in the models, imputation methods (e.g., multiple imputation) will be carefully applied as needed. The latter will be particularly important for the ITT analyses.

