smokeless use in men). Specifically, the main effect and interaction of each biological variable with intervention group will be tested. For each biological variable, statistically non-significant main and/or interaction effects will be omitted from the final analytic models. If there is a significant interaction (indicative of a moderating effect of the characteristic), the interaction and its component terms will be retained in the final model and a moderator analysis will be conducted applying the approach recommended by Kraemer et al.⁵¹ for clinical trials. For example, if there is a significant sex-by-group interaction effect, the moderating effects of sex will be further evaluated by testing for intervention effects within subgroups of the characteristic. We realize that our numbers of projected females for this study are small given nationally females use smokeless tobacco a very low rate (0.5%)¹¹ and our pilot mirrored these results. Nonetheless, we will conduct analyses to address the influence of these biological factors on study outcomes if there is adequate heterogeneity of the characteristic to do so.

[figure not shown]
Aim 1 Statistical Analysis. We will use logistic regression without covariates to test for an intervention group difference (SGR vs control) in self-reported cessation at 6 months. Next, a covariate-adjusted analysis will also be conducted to evaluate identified potential baseline covariates and examine the impact of biological variables (e.g., age and sex and their interaction with group) on self-reported cessation at 6 months. Odds ratios (ORs) and their 95% CIs will be used to estimate effect size and address clinical significance. As a supplemental analysis, Generalized Estimating Equation (GEE) models for longitudinal binary outcomes will be used to test for intervention group differences in cessation trajectories across the 6 months, with *a posteriori* contrasts at each assessment point. Finally, we will compare self-reported and biochemically confirmed cessation outcomes obtained from 20% random sample of those who self-reported cessation at end of treatment and month 3 and 6. A z-test will be used to test for a group difference in the percent agreement at each time point.

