will be evaluated separately (See **Figure 5**). First, the initial step of the formal mediation analysis will be to determine whether the intervention group significantly influences the trajectory of change in withdrawal symptoms, craving, self-regulation, and restraint (Path A). The Path A analysis will be completed in Aim 2. Second, logistic regression will be used to examine whether the slope coefficients for the individual trajectories of the proposed mediator are associated with cessation at 6 months (Path B). The final logistic regression model conducted for Aim 1 will be used to test for intervention group differences in cessation at 6 months post-intervention (Path C). Finally, the slope coefficients for the proposed mediator will be added as a covariate to the Path C logistic regression model (Path C'). The Path C' analysis will allow us to examine the effects of the intervention groups on Month 6 cessation after adjusting for the effects of change in the proposed mediator across time. For each proposed mediator of SGR effects, mediation will be established if the SGR group compared to the control group has significantly greater improvements in the mediator as an outcome (Path A), the degree of improvements in the mediator across time is related to cessation at 6 months (Path B), the SGR group has a significantly higher cessation rate at 6 months compared to the control group (Path C), and SGR effects on cessation are partially or fully diminished after adjusting for the mediator effect (Path C'). A Sobel's Test will be used to further determine the degree to which improvement in withdrawal, craving, self-regulation, and restraints mediate intervention effects. ORs and their 95% CIs will provide estimates of effect sizes.

Figure 5: Mediation Analysis Pathways

Statistical Power. The sample size of 500 (N=250 per intervention arm) will provide at least 90% power to address the primary aim (Aim 1), primary outcome (self-reported cessation at 6 months), and primary analysis (ITT analysis). A previous smokeless tobacco SGR study in smokeless tobacco resulted in a 27% cessation rate at 6-months.²⁵ Our pilot resulted in a 22% cessation rate at 6-months. Given the improvements to our

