SGR intervention, we conservatively estimate a slightly higher quit rate at 25% at 6-months. The Enough Snuff Control intervention has yielded quit rates between 16-18% at 6-months;^{43,44} however, these studies were clinic-based and deployed out of dental offices with military personnel, representing a different population and mode of delivery than we are proposing. A similar, web-based version of the intervention delivered remotely yielded quit rates of 12%.³⁰ Given the low-touch remote nature of our study and the focus on rural and underserved populations, we expect quit rates in the control group to be closer to 12% at 6-months. Therefore, we estimate a medium effect at 6-months. In summary, the target sample size is based on the assumptions that: (1) logistic regression will be performed with two-tailed significance set at 0.05; and (2) the quit rate at month-6 may be as low as 25% in the SGR group and 12% in the control group at 6-months for the ITT analysis (odds ratio of 2.44, Cohen's *d* equivalent of 0.493, approximate medium effect); Consistent with prior smokeless intervention studies, the target sample size will not be adjusted for attrition rate and dropouts will be coded as continued to use. Based on these assumptions, a sample size of 250 per arm will provide 96% power to test the primary aim. If an attrition rate of 30%

is observed in each arm of the proposed study, the resulting sample size of 175 per arm will provide at least 80% power for the completers analysis for Aim 1.

Addressing scientific rigor and reproducibility. All final study procedures will be documented in detail with accompanying scripts, documents, examples and measures. Our assessments and reports will include descriptive statistics. The study PI will oversee the training of study staff and make sure all procedures meet high standards of fidelity using a checklist of key tasks with periodic observations of performance of tasks. Facebook recruitment quality control will be maintained by [name] with consultation from [name]. Texting quality control standards will be maintained under the supervision of [name]. [name] will oversee quality control of all assessment measures during the study. Further, the study statistician, [name], will document data quality control standards and procedures (e.g., data checking).

Potential Risks and Challenges

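### The first Aim 1 test leaves out baseline nicotine dependence, which the protocol calls a predictor of quitting: a small missed efficiency in a valid test

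*SAP*

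**What the plan says.** The SAP, under Aim 1 Statistical Analysis, begins: "We will use logistic regression without covariates to test for an intervention group difference (SGR vs control) in self-reported cessation at 6 months". A covariate-adjusted analysis follows, using baseline covariates identified elsewhere together with age, sex and their interactions with arm.

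The SAP's Sample Characteristics paragraph says how those covariates are identified. Baseline variables are compared between arms, the comparison supplies the candidates, and non-significant ones are left out of the final models. Only age and sex are evaluated whether or not the arms differ, and they too are dropped if non-significant. No model names dependence in advance.

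The protocol's Significance section states: "Given nicotine dependence is a predictor of smokeless tobacco cessation". Dependence is measured with the SSTDS at all time points, and the baseline assessment precedes randomisation. The tobacco history collected at baseline includes "number of chews/dips per day, number of quit attempts in the past year". Randomisation uses permuted blocks of four, with no stratification factor named.

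On testing, the SAP says: "We will perform non-directional statistical tests with the significance level set at 0.05 for all analyses". Its Statistical Power paragraph assumes "the quit rate at month-6 may be as low as 25% in the SGR group and 12% in the control group at 6-months", gives an "odds ratio of 2.44", and concludes that "a sample size of 250 per arm will provide 96% power to test the primary aim".

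**The concern.** In a randomised trial, adjusting for a baseline variable that predicts the outcome removes explainable variation from the arm comparison and allows for chance imbalance in that variable. Here the protocol itself identifies such a variable and measures it before randomisation, but the first test does not use it. Nothing else in the plan reliably makes up for this. Randomisation does not balance dependence by design. A baseline-difference test at 0.05 would flag it only about 5% of the time under valid randomisation. Dependence will therefore usually enter no Aim 1 model, and whether it does will turn on chance imbalance, not on its value as a predictor.

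What is at stake is some precision and power. This matters little at the planned effect and more if the true effect is smaller.

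**Working it through.** **1. Reproduce the stated power.** Inputs from the SAP: 250 per arm, 25% vs 12%, two-sided 0.05. The mean rate is 0.185.

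z = [0.13·√250 − 1.96·√(2·0.185·0.815)] / √(0.25·0.75 + 0.12·0.88) = (2.0555 − 1.0763)/0.5414 = 1.809, so power is 96.5%. A Wald test on the log odds ratio gives 95.7%. The stated 96% holds. The odds ratio also reproduces: (0.25/0.75)/(0.12/0.88) = 2.44.

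**2. Variance removed by adjustment.** The documents give no predictor strength. I assume one standard-normal baseline score with an odds ratio for quitting of 1.25 to 2.5 per SD (area under the ROC curve about 0.56 to 0.73). Let m₁(X) and m₀(X) be the quit probabilities given the score in each arm, with intercepts set so that they average to the arm rates p₁ and p₀. With 1:1 allocation, the proportional reduction in the variance of the standardised risk difference is

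r = Var[m₁(X) + m₀(X)] / {2[p₁(1−p₁) + p₀(1−p₀)]}.

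At 25% vs 12%, the last column is 500/(1−r), the unadjusted trial size giving the same precision:

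| OR per SD | r | Equivalent total n |
|---|---|---|
| 1.25 | 0.7% | 504 |
| 1.5 | 2.4% | 512 |
| 2.0 | 6.5% | 535 |
| 2.5 | 10.7% | 560 |

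Simulation (20,000 trials per row) gave 0.4%, 1.6%, 5.5% and 10.7%.

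**3. Power gained.** Put 250/(1−r) per arm into the formula in step 1, recomputing r for each pair of rates. The smaller-effect pairs use figures in the documents: the pilot's 22% at 6 months in the SGR arm, and the 16% at the lower end of the control programme's published range.

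| Rates | Unadjusted | OR 1.25 | OR 1.5 | OR 2.0 | OR 2.5 |
|---|---|---|---|---|---|
| 25% vs 12% | 96.5% | 96.6% | 96.8% | 97.4% | 97.9% |
| 22% vs 12% | 84.7% | 85.0% | 85.5% | 87.0% | 88.4% |
| 25% vs 16% | 70.4% | 70.7% | 71.5% | 73.5% | 75.6% |

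The gains are 0.1 to 1.4, 0.2 to 3.6 and 0.3 to 5.2 points. Simulated Wald tests of the adjusted log odds ratio agree: at OR 2.5 per SD, power rose from 96.7% to 98.1%, from 84.9% to 88.4%, and from 71.4% to 76.5%.

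**4. What happens to the odds ratio.** In the 25% vs 12% simulation the unadjusted log odds ratio was about 0.90 with SE 0.245. The adjusted (conditional) value was 0.91 to 1.01 with SE 0.247 to 0.262. Its SE rises; power improves because the estimate moves further from zero (0.900/0.2454 = 3.67 against 1.013/0.2619 = 3.87 at OR 2.5).

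**5. Dilution by dropouts.** The SAP codes missing outcomes as not quit and considers 30% attrition. If 30% are missing independently of the score, each m becomes 0.7 times the completers' probability. At 25% vs 12%, r then falls from 6.5% to 4.8% (OR 2.0 among completers) and from 10.7% to 7.7% (OR 2.5).

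**The case against.** The strongest reply is that nothing is wrong. Unadjusted logistic regression is valid in a 1:1 randomised trial, and it matches the power calculation, which rests on the two quit rates alone. At those rates power is already about 96%, and the gain is at most about 1.4 points. Larger gains need both a smaller true effect and a strong predictor, and the documents establish neither. The pilot found no difference between completers and non-completers in baseline chews or dependence, so outcomes imputed as failures may be largely unrelated to dependence and weaken it further. All of this stands.

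Four stronger readings are tempting, and the documents do not support them:

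- A reader might infer that the primary test is faulty or the trial underpowered. The stated power reproduces.
- A reader might infer that the plan ignores covariates. It schedules an adjusted Aim 1 analysis, and a significant imbalance in dependence could bring dependence into it.
- A reader might infer that the protocol names several predictors. It names only dependence as one. Chews/dips per day is merely listed as tobacco history, and risky drinking is said only to have a possible influence on quit rates.
- A reader might infer that adjustment sharpens the plan's own odds ratio at no cost. Step 4 shows the opposite for the conditional odds ratio.

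Nor does the SAP declare the unadjusted model confirmatory. It labels the ITT analyses as primary, and Aim 3 refers to a final Aim 1 model without saying which that is.

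What survives is narrower. Prespecified adjustment for dependence uses data already collected, cannot be expected to lose power, and is not secured by the present plan.

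**Conclusion.** This is a small missed efficiency in a valid analysis, and an optional to recommended improvement. The precision gain should be claimed for the marginal effect only: about 1% to 11% of the variance of the standardised risk difference at 25% vs 12%. The corresponding power gain is negligible at the design rates, and reaches about 3.6 points at 22% vs 12% and about 5 at 25% vs 16% only with the strongest predictor considered.

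These sizes rest on an assumed predictor strength of 1.25 to 2.5 per SD and a correctly specified single score. They are probably nearer the low end once dropouts are coded as users. That the unadjusted model is the confirmatory one is inferred from sentence order.

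**What to change.** Under Aim 1 Statistical Analysis, name one confirmatory model: logistic regression with arm and baseline SSTDS score, optionally with baseline chews/dips per day. Fix the list in advance and do not screen it by significance.

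Take the primary p-value and 95% CI from the risk difference standardised to the whole randomised sample, and report the marginal odds ratio beside it. State the variance method, for example delta method or bootstrap, and how it combines with imputation of any missing baseline score, which the SAP already allows for covariates. Keep the unadjusted model as a sensitivity analysis, and say which Aim 1 model Aim 3 uses for Path C.

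The cost is a short SAP paragraph and some programming, with no new data or participants. The change should be made before anyone sees outcomes by arm.

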We will recruit smokeless tobacco users ($N=500$) and randomize them to receive the SGR intervention ($N=250$) or the Enough Snuff intervention ($N=250$). We will conduct phone-based or smart phone-based assessments with participants at baseline prior to randomization, end of treatment, 3 and 6-month follow-up after intervention completion. The primary outcome will be self-reported 7-day point smokeless tobacco use at 6-months (yes/no). We will biochemically confirm a subset of participants who report quitting via saliva samples using NicAlert test Strips (20% of sample who report quitting split between intervention and control group). NicAlert strips can be used with all tobacco types and have been used with smokeless tobacco users.³⁵ We will randomly select these participants at end of program, 3 and 6-month survey time points as to not confound intervention results. We will conduct a supplemental analysis to compare self-report and biochemically confirmed quit results. The secondary aims are to assess: 1) the efficacy of the text-based SGR intervention compared to the control intervention on changes in withdrawal, craving, self-regulation and restraint across the 6-month period and 2) explore whether changes in withdrawal, craving, self-regulation and restraint mediate intervention effects on self-reported cessation at 6 months post-intervention (Figure 2). We will follow participants regardless of whether they complete or adhere to the intervention.

Design Considerations. We chose our control comparator using guidance from the *Pragmatic Model for Comparative selection in Health Related Behavioral Trials*.³⁶ The main goal of our trial is to compare our new SGR intervention to a well established evidenced-based alternative like the Enough Snuff Intervention. We decided against adding nicotine replacement therapy or varenicline for smokeless tobacco users. A recent

Table 2. Lessons Learned from Pilot and Changes made to Proposal	
Areas for Improvement	Changes for Current Proposal
Length of time for accrual of our sample	Clinic recruitment was not feasible in our pilot. Once we switched to a social media recruitment approach, at the suggestion of [name] our metrics improved significantly. We plan to recruit solely using media outlets (including social media) and will expand our targeted recruitment area to increase reach. [name] will consult on recruitment in the current study.

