Follow-up assessments will be conducted over the phone or a smartphone option will be available for survey completion at the end of treatment, 3 and 6-months post-intervention. Study data collectors will be blinded to study arm. Our two research assistants will document who randomized each participant and will not conduct the follow-up assessment with those participants. We will obtain follow-up data on all participants regardless of adherence or completion of treatment. The follow-up rate in our pilot study was >70%, and we will use similar strategies to obtain follow-up data. To increase this follow-up rate, we also will maintain regular contact with participants in-between the end of program 3 and 6-month follow-up using cards, e-mails, and study updates summarizing study results. We will also use a graded compensation for surveys with \$10 for baseline \$15 for end of program, \$20 for 3 months and \$25 for 6-month follow-up. Participants will receive a bonus of \$25 for completing all assessments.

Randomization. The target sample will be eligible and enrolled participants randomized to either the SGR (N=250) or control (N=250) intervention group. Computerized randomization will be used to deliver a permuted block randomization with block sizes of four that will be used to randomly assign participants to one of the two intervention groups. The randomization scheme generated by the study statistician will be administered using the REDCap system.

Interventions:

SGR Intervention Group. We will send those in the SGR intervention group a 6-week text-based scheduled gradual reduction intervention and 6 weeks of support text-messages. Typical SGR interventions have lasted for 4 weeks. We have increased our program to 6 weeks based on feedback from our pilot.

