Self-report smokeless tobacco cessation will be assessed at the end of treatment, 3 and 6-months post-intervention. **Self-report smokeless tobacco cessation at month 6 will be the primary outcome.**

Secondary outcomes, which will be subsequently evaluated as mediators of the intervention effects, will be assessed at baseline, end of treatment, and 3 and 6-months post-intervention.

Primary Outcome: Smokeless Tobacco Cessation Outcome. Self-reported abstinence from tobacco use will be collected at end of treatment, 3 and 6-months post-intervention. We will measure 7-day point prevalence abstinence by asking participants, "In the past 7 days, have you used smokeless tobacco (chew or dip)?" This binary outcome will be dichotomized as 0=no and 1=yes. We will also randomly select a 20% (10% in control and 10% in intervention arm) of those who report quitting at the end of treatment, 3 and 6 months to biochemically confirm cessation using saliva cotinine strips. NicAlert Semiquantitative test strips will be used and a 10 ng/ml cutoff will indicate exposure. Biochemically validated cessation at each of these assessment points will be coded as 0=no and 1=yes.

Mediator: Craving. We will assess craving using the Smokeless Tobacco Evaluation Questionnaire (STEQ) based on the Cigarette Evaluation Questionnaire (mCEQ) modified for ST users.⁴⁶ The STEQ is a 12-item scale assessing the degree to which participants experience the reinforcing effects of smokeless tobacco on a 7-point Likert scale. The scale has five domains: chewing satisfaction, psychological reward, enjoyment of sensations in cheek/gum, craving reduction, and aversion.

Mediator: Withdrawal. We will assess withdrawal using the self-report seven item Minnesota Nicotine Withdrawal Scale⁴⁷ as has been used in other smokeless tobacco cessation trials assessing withdrawal. This seven-item scale measures withdrawal symptoms (i.e., irritability, anxiety, difficulty concentrating, restlessness, increased appetite or weight gain, depression, and insomnia) and measured on an ordinal scale (0= not present) to 4 (severe). A total score ranging from 0 to 28 will be derived to measure severity of withdrawal symptoms, with higher total scores representing greater withdrawal. Internal consistency of the scales are reported to be between $\alpha= 0.76-0.91$.

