Aim 2 Statistical Analysis. We will use hierarchical mixed-effects models for repeated measures with *a posteriori* contrasts at each time point to test for intervention group differences in the trajectory of changes in severity of craving, withdrawal, self-regulation, and restraints across time (baseline, end of treatment, 3 and 6 months post-intervention). Specifically, random coefficients regression model (RRM) for longitudinal data will be used to compare the rate and pattern of change of these outcomes across time. Fixed effects will be intervention group, time, and group-by-time, while random effects will be participant and participant-by-time. A covariate-adjusted analysis will also be conducted to evaluate the influence of baseline covariates and biological variables (e.g., age and sex effects and their interactions with group). The model will be fitted for significant non-linear change within one or both intervention groups. Intraclass coefficients across time along with Cohen *d* equivalents and their 95% CIs at each time point will be used to address intervention effect sizes.

Exploratory Aim 3 Statistical Analysis. We will conduct mediator analyses using criteria recommended by Baron and Kenny⁵² as well as analytic guidelines from Kraemer et al.⁵¹ to explore whether changes in withdrawal symptoms, craving, self-regulation, and restraint mediate intervention group effects on tobacco use cessation across the 6-months. Each proposed mediator

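### The Aim 2 mixed model gives each arm its own baseline mean; a common baseline mean would sharpen the secondary contrasts using data already collected

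*SAP*

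**What the plan says.** The SAP, Aim 2 Statistical Analysis, compares the arms on craving, withdrawal, self-regulation and restraint "across time (baseline, end of treatment, 3 and 6 months post-intervention"), so baseline is a response row. The model terms are: "Fixed effects will be intervention group, time, and group-by-time, while random effects will be participant and participant-by-time". The outputs are "contrasts at each time point to test for intervention group differences", the rate and pattern of change, and Cohen d equivalents with intervals at each time point. The same section adds a covariate-adjusted analysis and provides for non-linear change.

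The Protocol, Overall Strategy, schedules "assessments with participants at baseline prior to randomization, end of treatment, 3 and 6-month follow-up after intervention completion". Its Measures section says the secondary outcomes "will be assessed at baseline, end of treatment, and 3 and 6-months post-intervention". Allocation is by "permuted block randomization with block sizes of four", with equal arms.

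The SAP, Sample Characteristics, chooses candidate covariates by testing for baseline differences between arms and drops those that are not significant. The SAP, Exploratory Aim 3, takes Path A from the Aim 2 model and uses each participant's trajectory slope in Paths B and C'.

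**The concern.** A group main effect, with baseline among the responses, estimates a separate baseline mean for each arm. Randomisation makes the true baseline difference zero, so the model spends information estimating a known quantity. The baseline score then does less than it could to reduce noise in the follow-up comparisons.

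The loss falls on all four secondary outcomes. It also reaches Aim 3, because mediation is declared only if Path A shows a significant arm difference in the mediator's trajectory. The SAP states no power for Aim 2, so there is no documented margin to absorb the loss.

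The planned covariate adjustment does not settle the matter. It is an additional analysis, it does not name the baseline value of the outcome, and its covariates are screened on significance. The precision gain comes from the correlation of baseline with follow-up, not from imbalance. A baseline score that is balanced between arms, as most will be, could therefore be screened out although it would help.

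**Working it through.** **The plan's own figure.** The only power statement is for Aim 1: 250 per arm, 25% against 12%, two-sided 0.05. The pooled proportion is 0.185. The null SE is √(2×0.185×0.815/250) = 0.0347, and the alternative SE is √((0.25×0.75 + 0.12×0.88)/250) = 0.0342. Then (0.13 − 1.96×0.0347)/0.0342 = 1.81, giving 96.5% against the stated 96%. It reproduces, and nothing below affects it. For Aim 2 the documents give no SD, effect size, correlation or power.

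**Visit contrast.** Inputs: n = 250 per arm (SAP, Statistical Power), SD = 1, and an assumed correlation r between baseline and the visit.
- Free baseline means: variance = 2/n = 0.0080, SE 0.0894.
- Common baseline mean: variance = 2(1 − r²)/n.
- Detectable difference at 80% power = (1.96 + 0.84) × SE.

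| r | SE, free | SE, common | Variance cut (r²) | Detectable difference (SD) |
|---|---|---|---|---|
| 0.3 | 0.0894 | 0.0853 | 9% | 0.251 → 0.239 |
| 0.5 | 0.0894 | 0.0775 | 25% | 0.251 → 0.217 |
| 0.7 | 0.0894 | 0.0639 | 49% | 0.251 → 0.179 |

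At 175 per arm (the SAP's 30% attrition case) and r = 0.5, the detectable difference goes from 0.300 to 0.259 SD.

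**Slope and change contrasts.** With two time points and equal variances, the variance ratio against a change-score contrast is (1 − r²)/(2(1 − r)) = (1 + r)/2, a cut of 35%, 25% and 15% at the same r. This does not carry over to the SAP's model, whose participant-by-time random effect makes the variance change over time. I therefore used generalised least squares on a random intercept-and-slope model. The covariance is V = ZGZ′ + σ²I, the information is n Σ X′V⁻¹X over the two arms, and the contrast variance comes from its inverse, with the baseline group term either present or removed.

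Assumptions: visits at 0, 1.5, 4.5 and 7.5 months; baseline variance 1; intercept share 0.3, 0.5 or 0.7; no intercept-slope covariance; complete data. The visit column uses categorical time and the slope column linear time.

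| Intercept share | Slope variance ÷ intercept variance | r, baseline to month 6 | Variance cut, month-6 visit | Variance cut, slope |
|---|---|---|---|---|
| 0.3 | 0 | 0.30 | 9.0% | 33.6% |
| 0.3 | 0.01 | 0.28 | 7.7% | 29.4% |
| 0.3 | 0.10 | 0.18 | 3.3% | 13.9% |
| 0.5 | 0 | 0.50 | 25.0% | 21.5% |
| 0.5 | 0.01 | 0.44 | 19.5% | 16.2% |
| 0.5 | 0.10 | 0.26 | 6.6% | 5.0% |
| 0.7 | 0 | 0.70 | 49.0% | 11.7% |
| 0.7 | 0.01 | 0.59 | 35.2% | 6.6% |
| 0.7 | 0.10 | 0.32 | 9.9% | 1.3% |

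The visit cut equals r² in every row. The slope cut depends on the variance components, not on r alone. In the last row r = 0.32, where the two-point formula would give (1 − 0.32)/2 = 34%, against 1.3% here. The 33.6% is a limiting case with no slope variation between participants.

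With 30% dropout (10% lost before each follow-up), the common-baseline model still had the smaller variance throughout. For example, at an intercept share of 0.5 and a ratio of 0.01, the cuts are 15.0% for the visit and 14.4% for the slope.

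**The case against.** Group, time and group-by-time with baseline as a response is a conventional and valid specification, and Aims 2 and 3 are secondary and exploratory. That stands, and it limits the point to efficiency.

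Three stronger readings are tempting, and the documents support none of them.
- **That the visit contrasts are biased by chance baseline imbalance.** Over randomisation the planned contrasts are unbiased, and chance imbalance is already reflected in their standard errors. Under a random-coefficients model with continuous time they are also not raw visit means, since they borrow from all four visits.
- **That the loss equals a fixed share of the sample.** At r = 0.5 a 25% variance cut corresponds to 1/0.75, or 33% more participants. That rests on one assumed correlation and on the visit contrast; for the slope the gain can be close to nil.
- **That any form of baseline adjustment would serve, at no cost.** Modelling only the three follow-ups, with baseline as covariate, would take the change from baseline to end of treatment out of the individual slopes used in Paths B and C'. That alters the Aim 3 mediator.

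It is also fair to say that a marked imbalance in a baseline score might be caught by the covariate screen. This is possible but not assured, and it would not deliver the gain when the arms are balanced.

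**Conclusion.** The point holds as lost precision in a valid secondary analysis. The Aim 2 model estimates a baseline difference that randomisation sets to zero in expectation. A common baseline mean gave a smaller variance in every scenario tried. For a visit contrast the variance cut is roughly r², or 9% to 49% for r from 0.3 to 0.7. For the slope or change contrast it runs from about 1% to about 30%.

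These sizes rest on assumed correlations, visit times and variance components, because the documents supply none; the direction does not depend on them. Aim 1 and its power are untouched. Priority is lower: a free improvement, not the correction of an error.

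**What to change.** In the SAP's Aim 2 section, keep baseline in the response and constrain the arms to a common baseline mean. Code time as 0 at baseline, include no group effect there, and fit group-by-time terms at the three post-baseline visits. Use categorical time or the planned non-linear terms. Deleting the group term from a straight-line model would force the effect to grow in proportion to time since baseline.

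Take the visit contrasts, Cohen d values and Path A test from this model. Do not also enter the baseline score as a covariate. Keep the participant-level random effects so that the Aim 3 slopes still span baseline to month 6, and state how those slopes are derived if time is categorical in the fixed part.

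The cost is a short SAP edit and a changed model statement, made before any comparison by arm is seen. No new data, visits or participants are needed.
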